10.5.3 Cardiovascular and Bone Fracture Risk Biomarkers

The combination of high sensitivity C-reactive protein and total cholesterol:HDL ratios provide excellent risk biomarkers for cardiovascular disease [Ridker 2005]. Lipid panel with total cholesterol:HDL ratio is performed on serum by an enzymatic assay after a 12 hour fast. High sensitivity C-reactive protein, an indicator of inflammation, will be performed by an immunochemiluminometric assay.

N-telopeptide crosslinks correlate with the rate of bone reabsorption and bone mineral density in osteoporotic women and can be used to monitor the efficacy of anti-reabsorptive therapy with estrogen and calcium [Greenspan 2000]. The test is performed on serum by EIA. Mean values for women are 12.6 nM BCE/L (6.2 – 19.0 nM BCE/L).

Osteocalcin is a measure of bone/reabsorption. It together with the N-telopeptide is helpful in determining reduction in bone turnover in response to anti-reabsorptive agents or predicting early bone mineral loss after hormone therapy is stopped. The test is performed on serum by an immunochemiluminometric (ICMA) assay [Slovik 1984]. It is best performed fasting as it cannot be performed on a lipemic specimen.

The above assays will be performed at LabCorp Inc. Research Division or a similar CLIA-approved laboratory.

Estrogen supplementation increases high density lipoproteins and thus it is possible that administration of letrozole will result in a higher total cholesterol:HDL ratio. We do not expect any difference in change in C-reactive protein, osteocalcin, or N-telopeptide between letrozole and placebo groups.

10.5.4 Serum 25-OH Vitamin D Levels

The cause of the increase and/or induction of joint stiffness and arthralgias in women taking aromatase inhibitors is not clear but may be due to estrogen deprivation in combination with suboptimal vitamin D levels. Blood levels of 25-OH vitamin D are a good measure of vitamin D adequacy and for optimum bone and general health should be in the 32-50 ng/ml range [Vieth 1999; Holick 2003; Heaney 2004]. Suboptimal or deficient levels of 25-OH vitamin D are common in postmenopausal women, ranging from 25 to 50% of those tested when 37 ng/ml is used as the lower cutoff [LeBoff 1999; Aguado 2000; Glowacki 2003]. Persistent pain, particularly in shoulders, wrists, hips, knees, legs, and ankles, as well as joint stiffness has been reported in 93% of individuals with 25-OH vitamin D levels <20 ng/ml [Plotnikoff 2003]. Taylor et al. has recently reported in abstract form that a high proportion of postmenopausal women on AIs with musculoskeletal complaints had vitamin D deficiency [Taylor 2004]. We will assess the effect of baseline and follow-up 25-OH vitamin D levels on subsequent development of arthralgias.

All samples will be run in KUMC's clinical laboratory by a widely used RIA kit [Gunter 1988-1994]. The assay limit of detection is 1.5 ng/ml. Assay precision varies only slightly with vitamin D level from 8.6 to 12.5% for run-to-run variation and 8.2 to 11% for between-run variation.

We do not expect any increase or decrease in 25-OH vitamin D levels other than that expected from seasonal variations. However, low 25-OH vitamin D levels may explain development of arthralgias or an increase in bone turnover if encountered in women randomized to letrozole.

10.6 Breast Density Measurements

Mammograms will be performed within three months of the baseline aspiration and at six and twelve months. An attempt will be made to use the same machine at baseline and at 6 and 12 months. However, it is imperative that a woman has breast imaging performed on either analogue or digital for all three imaging procedures. Either copies of the mammograms or direct digital files will be sent to KUMC from collaborating sites for assessment of breast density. For assessment of mammographic breast density from analog films, the right and left cranial caudal views will be digitized using a Lumiscan 85 film digitizer.

These films will be used for a blinded assessment of breast density parameters using the Cumulus software program [Boyd 1998; Boyd 1997]. Both [name] and [name] have been trained by [name] in Toronto in the use of this method. Specifically, [name] achieved >85% agreement with [name] on training.

Prior to the analysis, images will be checked to make sure cropping (total breast volume) is similar. For the analysis, dates will be removed so the reader will not know which is the baseline and which is the 6 or 12 month film, but the three will be analyzed in the same batch. Stone et al have recently reported that the method of analysis with the least intraobserver variance is for the reviewer to view the initial and the follow-up mammograms together, but with the reviewer blinded as to which is the baseline and which is the follow-up study [Stone 2003] Both the absolute area of increased density and proportional density (area of increased density divided by total area of breast) will be assessed.

10.7 Quality of Life Evaluations

The most frequent adverse events in our pilot trial were arthralgias, fatigue and hot flashes. Consequently, in addition to utilizing the Breast Cancer Prevention Trial (BCPT) symptom scale (used as part of NSABP prevention trials) [Ganz 1995; Day 1999], we will use specific tools geared to the most prevalent symptoms in the pilot study.

The BCPT symptom checklist is a 42 item list of problems common to peri and postmenopausal women and those undergoing anti-hormonal

treatment in prevention trials. Women are asked if they have had the symptom in the past four weeks. If they answer yes, they are asked to grade the severity (0-4). This tool can be used to compute a total score or individual or related items of interest (e.g., three items relate to joint stiffness and arthralgias) may be scored [Stanton 2005].

The Mayo Clinic Hot Flash scoring system was developed by Loprinzi et al. Subjects are asked about their daily number of hot flashes and rate usual severity from 1 to 4. The frequency is multiplied by usual severity to obtain a total score [Loprinzi 2002].

We do not expect an increase in symptoms or hot flash scores for women randomized to letrozole.

The Fibromyalgia Impact Questionnaire (HAQ) is a validated tool routinely used by rheumatologists to evaluate pain, stiffness, and physical functioning. Individual domains or a total score can be utilized in assessment [Wolfe 2004].

The brief fatigue inventory asks the woman to rate her current as well as worst and usual fatigue in the past 24 hours. It also asks her to rate how the fatigue has affected mood, general activity, walking, work relations, and enjoyment of life [Mendoza 1999].

We do not expect an increase in joint pain, stiffness or fatigue for women randomized to letrozole, unless a woman has suboptimal levels of 25-OH vitamin D.

11.0 DATA MANAGEMENT

Participant data will be collected using protocol-specific case report forms (CRF) developed by KUMC. A copy of all documents up to the month six visit will be mailed to KUMC as soon as they are completed, and the remainder as soon as the subject completes study.

Information for data analyses will be entered by site trial coordinators from source document onto Case Report Forms (CRFs). Data items from the CRFs will be entered into the the web-based CRIS study database by KUMC.

Source document files/chart must be kept available at sites for monitoring visits during the conduct of the study through data analysis.

Subsequently, the information entered into the database will be systematically checked by Data Management staff. Other errors or omissions will be entered on Data Query Forms, which will be returned to the site trial coordinators for resolution. Data queries must be addressed and returned to KUMC within 14 days of submission to site.

Laboratory data from RPFNA and blood analysis perform at KUMC will be entered on source documentation, entered into a database and reviewed by accuracy by KUMC study staff.

Co-existent disease and adverse events will be coded using the NCI CTCAE, version 3.0.

When the database has been declared to be complete and accurate, the database will be locked. Any changes to the database after that time can only be made by joint written agreement between the Protocol Chair, the Trial Statistician and the Data Manager.

11.1 Source Documents

Source documents will consist of reports (mammogram reports, laboratory reports, etc.), and forms created specifically for this study that will capture information such as physical exam, phone contact information, adverse events, concomitant medications, demographics, etc. To the extent which possible, source documents (aside from reports) will be formatted to be similar to the CRF format, in order to make the transcription from source to CRF more reliable. Special laboratory CRF's will be created to capture biomarker laboratory data including cytomorphology, nuclear morphometry mammographic density, Ki-67, serum hormone levels, osteocalcin, C-reactive protein, fasting lipid profile and 25-OH vitamin D levels. Data will be entered in an Excel spread sheet which can be merged with the database held at KUMC.

11.2 Data and Safety Monitoring Plan

Prior to activation of the clinical trial, a Data Safety and Monitoring Committee (DSMC) will be established. The DSMC will consist of four members that will be identified later: a clinical faculty member at KUMC, a member of the Clinical Trials Division of the Kansas Cancer Institute, and

two external members with experience in clinical prevention trials. One member will be selected by the Committee to serve as Chairman for administrative purposes.

The DSMC monitors data management, subject safety, and subject accrual. The DSMC also provides advice on the overall conduct of the study. Meetings will be held by phone on an annual basis. Interval conference calls may be conducted as required. The functions of the DSMC are primarily those of an overview nature in regard to both data and safety, as detailed below.

All data collected for this trial will ultimately reside in a central database. The sources of data are three-fold: (1) All clinical data that originate at KUMC or collaborating sites are entered onto specific Case Report Forms (CRFs). The CRFs will be audited and source documents reviewed by a central multi-site monitor, after which the CRFs will be sent to KUMC. The data are entered into the central database and audited/validated. Periodically, these data are output to individual subject summary sheets so as to allow periodic assessment by the Protocol Chair ([name]) and staff. (2) Biomarker data from the assessments at KUMC of fine needle aspiration specimens (cytologic characterization, cytology score, and Ki-67 and ER immunocytochemistry score) and mammographic breast density are entered onto trial specific CRFs. Data are then entered into a trial specific central database. There are appropriate checks (such as comparison of electronic files to validated paper printouts) on data accuracy and completeness for all sources of data. This is accomplished via inspection of summary reports prepared for the DSMC by the biostatistician for this project, [name].

The subject cohort consists of essentially healthy women who are defined as being at high risk for the development of breast cancer, but do not have any clinical evidence of or suspicion for an existing malignancy. As such, side effects that might be due to the study intervention are expected to be minimal but should be easily identified and monitored.

In regard to adverse events (AEs) or serious adverse events (SAEs), it is not deemed necessary for the DSMC to address these for individual subjects. Rather, all grade 4 toxicities are reported as an SAE to the institutional review board immediately.

In addition to the functions listed above, the DSMC may serve in a general advisory role in regards to assessing the progress that is being made on the study. Subject accrual rates, and specifically problems with accrual that might impact on the ability of the trial to be completed, can be addressed by the DSMC. Likewise, the committee may make suggestions on other aspects that would improve the quality of the trial.

11.3 Sponsor or FDA Monitoring

The NCI, DCP (or their designee), pharmaceutical collaborator (or their designee), or FDA may monitor/audit various aspects of the study. These monitors will be given access to facilities, databases, supplies and records to review and verify data pertinent to the study.

11.4 Record Retention

Clinical records for all participants, including CRFs, all source documentation (containing evidence to study eligibility, history and physical findings, laboratory data, results of consultations, etc.), as well as IRB records and other regulatory documentation will be retained by the Protocol Lead Investigator ([name]) in a secure storage facility in compliance with HIPAA, OHRP, FDA regulations and guidances, and NCI/DCP requirements unless the standard at the site is more stringent. The records for all studies performed under an IND will be maintained, at a minimum, for two (2) years after the approval of a New Drug Application (NDA). The records should be accessible for inspection and copying by authorized persons of the Food and Drug Administration. If the study is done outside of the United States, applicable regulatory requirements for the specific country participating in the study also apply.

12.0 STATISTICAL METHODS

The study is a Phase II, double-blind, randomized, placebo-controlled clinical trial to assess the potential efficacy of letrozole as a chemopreventive agent, as measured by changes in proliferation index (Ki-67) between baseline and 6-months. Secondly, the study will evaluate other pharmacodynamic properties of the agent and assess which biomarkers, if any, are modulated. Side effects, adverse events, and quality of life will also be assessed.

Standard randomization strategies will be employed with type of HRT (E vs E+P) as the only stratification factor other than institutional site so that each site can be provided with a unique randomization schedule at initiation. All eligible subjects will be randomly assigned to letrozole or placebo in a 1:1 ratio.

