2.2.4.4 Risks and Benefits of Hormone Replacement Therapy

Hormone replacement therapy, while associated with a reduction in menopausal symptoms, osteoporosis and hip fracture as well as colon cancer, is also associated with increased risk of breast cancer and venous and arterial thromboembolism [Rossouw 2002; Anderson 2004; Hays 2003; Peeyananjarassri 2005]. Risk varies with type, dose and route of drug administration as well as age of the individual. For breast cancer, the increase in relative risk is 1-2% per year of use for estrogen alone, and 5-10% per year for estrogens plus progestins [Chlebowski 2003; Anderson 2004; Beral 2003; Fournier 2005]. No increase in risk of breast cancer has been demonstrated for women who began oral premarin alone in their 50's and continued for an average of eight years [Chlebowski 2003]. Increase in risk of breast cancer applies to current users only and may be less for micronized progesterone than a synthetic progestin in women taking combination therapy [Fournier 2005].

Increase in risk of cardiovascular events and deep venous thrombosis appear to be related to route of administration, type of preparation as well as a woman's age. Increase in deep venous thrombosis and cardiovascular events and dementia is probably due to the procoagulant effects of oral estrogen and progestins promoted by increased production of thrombophilic proteins as a result of a first pass effect of estrogen through the liver [Anderson 2004].

Younger women ages 50-60 on estrogen alone may actually experience a reduction in coronary disease risk due to the favorable properties of estrogen on vascular endothelium [Anderson 2004; Hsia 2006; Blumel 2003]. There appear to be fewer procoagulant effects [Modena 2005; Langer 2005] and thromboembolic events [Oger 2003; Scarabin 2003] with transdermal compared to oral preparations. C-reactive protein along with lipids are powerful predictive biomarkers for future cardiovascular events among healthy women [Ridker 1998, 2005]. Specifically the increase in C-

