After six months of letrozole, a reduction in Ki-67 was observed in 31/42 (74%) subjects, while continuing with baseline hormone replacement. The median pre- and post-study Ki-67 was 4.0% and 1.5%, respectively (Table 1). The mean absolute change in Ki-67 was -2.3%, with 95% confidence intervals (-4.2% to -0.8%) which did not encompass zero. The median relative change was -66% of the baseline values. Reduction in Ki-67 was observed for 27 of the 35 subjects taking estrogen alone and for 4 of the 7 subjects taking estrogen plus a progestin. As an example of the robust response possible with 6 months of letrozole, Figure 3 shows cytology and Ki-67 expression for the pre-study and post-study RPFNA specimens. For this subject, not only was cytology changed from hyperplasia with atypia to simple hyperplasia, but Ki-67 was reduced from 13.2% to almost 0.

Figure 3: Effect of 6 Months of Letrozole

[figure not shown]
Our results differ from those published by Harper-Wynne et al. for a small pilot study of letrozole [Harper-Wynne 2002]. They found no significant decrease in Ki-67 after 12 weeks of letrozole in core biopsy specimens of benign breast tissue from high risk postmenopausal women. However, their median baseline Ki-67 was only 1.25%. Seven of our subjects had a Ki-67 <1.5%. Six of these seven exhibited no decrease after six months of letrozole. This underscores the inability to detect change at very low levels of Ki-67 as has been reported by others [Harper-Wynne 2002; Dowsett 2005A].

Six subjects had essentially no baseline staining for ER in areas of hyperplasia (ER IS score <0.10). Baseline Ki-67 ranged from 0.8 to

23.6%, and Masood scores from 14 to 16 in these subjects. All subjects without baseline ER expression, except one who also had a low baseline Ki-67 of 0.8%, exhibited a dramatic reduction in Ki-67 at six months. These findings in benign breast tissue are similar to those of Miller et al. [Miller 1987] and Yue et al. [Yue 2001] who found that aromatase expression is similar in ER- and ER+ breast cancer; and that aromatase activity is a stronger predictor of clinical response to AIs than is ER [Miller 1987, 2001].

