6.13 Registration/Randomization/Consent

Potential subjects will be registered for the screening portion of the study by site study coordinator and principal investigator on a site screening log. Potential subjects will be given a unique screening number by the site staff and this will be affixed to all eligibility specimens and documents that will be sent to KUMC for review. No PHI should be attached to these items.

Site staff will not randomize a subject until verification by KUMC Trial Coordinator by means of a faxed request (standard form provided for this purpose which will include an eligibility checklist and notification of acceptable consent) for a particular potential subject. The designated KUMC Trial Coordinator will fax back to the Site Coordinator an approval to randomize the subject based on the review of the eligibility checklist provided by the site.

Approved eligible subjects will be randomized by a randomization schedule at each site, prepared and provided by the Study Statistician. The site staff and subjects will be blinded as to the assignment to drug or matched placebo.

The subject will be assigned a randomization number, after stratification by site and type of hormone replacement therapy. The randomization schedule will be stratified by site (each site will be provided a unique list for use only at that site), and whether the subject is on an estrogen preparation alone, or estrogen plus a progestin preparation. Randomization will be in sequential order according to the randomization list provided. Subjects approved for randomization will be assigned a site specific randomization number, consisting of four digits. The first digit will identify the site (to be determined later) and three digits identifying the specific potential subject.

Sub-contracted sites other than KUMC may use the study consent for the screening RPFNA, or use a research/clinical consent for that purposes. Subjects are not officially on study until they have made it through the entire eligibility process. KUMC will use the High Risk Protocol Consent (KUMC HSC#4601) for the purposes of the screening RPFNA.

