12.2 Statistical Analysis

All analyses will be intent-to-treat. All subjects randomized will be evaluable for safety and all subjects that have both a pre and post specimen are evaluable for efficacy. Primary analysis of efficacy will be performed on all evaluable subjects and secondary analysis will be done on those subjects who received at least 3 months of study medication. From our experience we have very little missing data, however, if the missing data rate is above 5%, we will use multiple imputation to impute these values to perform the primary and secondary analyses.

The primary outcome will be change in Ki-67 (percent of cells expressing Ki-67) from baseline to 6 months. The two-sample t-test will be used to compare the change in Ki-67 between the letrozole and placebo groups. Any difference in baseline values of Ki-67 between the two groups would

be due to chance, however, if there is a significant difference, then analysis of covariance adjusting for baseline values will be performed. Due to potential skewness in these variables we will assess whether or not the Central Limit Theorem may be assumed. Given the sample size the existence of an extremely high degree of skewness would require the use of the Wilcoxon Signed Rank test.

For the secondary endpoints, similar methods as above will be used to compare the treatment and control groups at two time points for all markers, i.e., serum hormones, mammographic breast density, and clinical laboratory tests. We will also correlate change in the primary biomarker Ki-67 with change in other markers (e.g., bioavailable estradiol, pS2, GREB-1) using Pearson's correlation coefficient. Again, if there exists a high degree of skewness in these variables, Spearman's correlation will be utilized.

Multiple regression analysis will also be used to investigate whether changes in Ki-67 are due to variables other than treatment effect (e.g., age, cytomorphology, Gail risk; as well as the predictive effect of other biomarkers on modulation of Ki-67). Best subsets and stepwise approaches will be employed while controlling for treatment group.

For comparison of moderate or worse toxicities we will consider grade 3 toxicity or premature trial discontinuation as the critical events. The prevalence of events in the letrozole vs. the placebo arm will be examined by Fisher's exact test.

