Evaluation of drug-induced hormonal changes - We will examine whether Letrozole has any effects on serum levels of bioavailable estradiol, and testosterone, determined at baseline and after six months of study medication. We will determine whether addition of letrozole alters the frequency of menopausal symptoms.

Adverse Events and Quality of Life – Change from baseline to six months for hot flash score (Mayo Clinic), fatigue (brief fatigue inventory), overall quality of life (BCPCT), bone turnover markers, HDL/total cholesterol, and C-reactive protein will be compared between the two groups using the two-sample t-test. Similarly, demographic variables (e.g., age, education) and hormonal levels will be tested for use as covariates on each of these endpoints. We will also assess the effects of change in serum hormones (if any) and baseline 25-OH vitamin D levels on incidence and severity of arthralgias and fatigue.

Within Letrozole Comparisons at baseline, 6 and 12 months - On all of our quantitative continuous measures we will perform a repeated measures analysis comparing the 6 and 12 month values to baseline and also with each other. This will give us some preliminary indication whether there is any benefit or detriment of 12 months of treatment. For all the above analyses of exploratory endpoints, as well as for changes in proliferation, results from the 12-month timepoint (following six months of open-label treatment with active agent) will also be analyzed and compared to the baseline and six month values with caution since the double-blind, randomized nature of the comparison is no longer present. However, since

every effort is made to conduct the assessment and quantification of biomarkers without knowledge of treatment arm, the results could be informative.

Since this is a phase IIB trial, the power and sample size for the primary endpoint was determined with a two-sided type I error rate of 5%. All subsequent secondary, tertiary and exploratory analyses will also be tested with a two-sided type I error rate of 5%. This may result in an elevated false positive rate for these secondary and tertiary analyses, however, since this is a Phase IIB study, we felt to control the type I error rate for the secondary, tertiary and exploratory analyses would be too conservative.

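### Randomisation is stratified by HRT type and site, but section 12.2 prespecifies neither factor in any analysis and commits to no estimate by HRT type

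*Combined protocol and SAP*

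**What the plan says.** Two sections describe the same stratification. Section 12.0: "Standard randomization strategies will be employed with type of HRT (E vs E+P) as the only stratification factor other than institutional site". Section 6.13 gives each site its own list and stratifies further by "whether the subject is on an estrogen preparation alone, or estrogen plus a progestin preparation".

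Section 12.2 then sets out the analyses:

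- Primary: "The two-sample t-test will be used to compare the change in Ki-67 between the letrozole and placebo groups".
- The only adjustment named for the primary endpoint is conditional. If baseline Ki-67 differs significantly between arms, "analysis of covariance adjusting for baseline values will be performed".
- An exploratory regression, with best-subsets and stepwise selection and treatment kept in the model, looks at "variables other than treatment effect (e.g., age, cytomorphology, Gail risk; as well as the predictive effect of other biomarkers on modulation of Ki-67").
- For symptom, quality-of-life and safety-marker endpoints, "demographic variables (e.g., age, education) and hormonal levels will be tested for use as covariates on each of these endpoints".

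HRT type and site appear in none of these. There is no stratified test, no stratum covariate, no estimate by HRT type and no treatment-by-HRT-type interaction.

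**The concern.** HRT type is the one clinical characteristic that the design balances on, so the plan evidently regards it as possibly related to outcome. An analysis that leaves it out gives back the precision that the balancing was meant to buy.

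The second loss is information. Section 1.0 expects the trial to support a large study in high-risk women who need hormone replacement, with no restriction by regimen. Section 2.2.4.4 separates the regimens on breast cancer risk: "the increase in relative risk is 1-2% per year of use for estrogen alone, and 5-10% per year for estrogens plus progestins". The pilot report in section 2.8 also split its Ki-67 result by regimen. The randomised trial, which unlike the single-arm pilot has a placebo group in each regimen, makes no commitment to do the same. Readers would have an overall difference with no statement of how much, or how little, it says about women on estrogen plus a progestin (E+P).

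**Working it through.** **1. The plan's own figure.** Inputs from section 12.1: difference 3.7 points, SD of change 5.5, two-sided 5%, 48 per arm. The exact noncentral-t power is 90.4% (90.1% at the rounded 0.67 SD). The stated 90% with 96 evaluable women reproduces.

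**2. Precision lost by omitting HRT type.** The E+P share f is taken from the pilot in section 2.8: 7/42 = 1/6. The documents give no difference d in mean change between HRT types, so d = 2 to 4 points is an assumption.

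The share of variance explained by the stratum is R² = f(1−f)d²/5.5², with f(1−f) = 5/36 = 0.139. The excess of the unadjusted standard error over that of the model with a stratum term is 1/√(1−R²) − 1. If d exists only under letrozole, the stratum main effect is d/2, that is 1 to 2 points.

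| Where the difference exists | Main effect | R² | SE excess |
|---|---|---|---|
| Both arms, d = 2 | 2 | 0.556/30.25 = 1.8% | 0.9% |
| Both arms, d = 4 | 4 | 2.222/30.25 = 7.3% | 3.9% |
| Letrozole only, d = 2 | 1 | 0.139/30.25 = 0.5% | 0.2% |
| Letrozole only, d = 4 | 2 | 0.556/30.25 = 1.8% | 0.9% |

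**3. Validity of the unstratified test.** Under stratified randomisation the t-test's true two-sided size is approximately 2[1 − Φ(1.96/√(1−R²))]. For R² = 1.8% this is 4.8%, and for 7.3% it is 4.2%. The test is conservative. Power with the stratum in the model, replacing 5.5 by 5.5√(1−R²), is 90.9% and 92.3%, so 96 women remain enough.

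**4. What an E+P estimate could show.** At the pilot share, 96/6 = 16 women, about 8 per arm.

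- 95% CI half-width: t(14) × 5.5 × √(2/8) = 2.145 × 2.75 = 5.9 points, against a target of 3.7.
- Power for a 3.7-point effect in that stratum: about 24%.
- Power for a 3.7-point interaction, with SE 5.5 × √(2/8 + 2/40) = 3.01: about 23%.

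**5. What the overall test would miss.** Suppose, purely as an illustration, that letrozole had no effect in that sixth. The average effect would be 3.7 × 5/6 = 3.08, and overall power would still be about 78%. A positive overall result is therefore compatible with no effect in E+P users.

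**6. The pilot split.** Section 2.8 reports a fall in Ki-67 in "27 of the 35 subjects taking estrogen alone and for 4 of the 7 subjects taking estrogen plus a progestin", that is 77% and 57%; Fisher's exact p = 0.35. Non-responders number 8 + 3 = 11. The same section says that seven pilot women had baseline Ki-67 below 1.5% and that six of them showed no decrease. Section 4.3 requires at least 1.5%, so six of the 11 non-responders would not be enrolled here. All three E+P non-responders could be among those six. The sub-analysis of 33 women in section 2.8 (28 with a fall) gives no split by HRT type.

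**The case against.** The strongest reply is that nothing is invalid and little is lost. That largely stands. Ignoring the strata makes the test slightly conservative, and the standard-error excess is at most a few per cent under assumed differences whose upper end exceeds the treatment target itself. It is also fair that no objective in section 1.0 asks for an effect by regimen, and that 96 women cannot supply a firm one.

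A reader might infer three stronger things that the documents do not support.

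- That the pilot showed letrozole working less well with E+P. Most women fell in both groups, the contrast is inconclusive, and it includes women whom this trial excludes. A single-arm pilot also cannot separate a different letrozole effect from a different natural course.
- That HRT type will never be analysed. The regression covariates are given only as examples, so HRT type may be examined. The accurate statement is that it is not prespecified; entry by stepwise selection is not a planned result by regimen.
- That a result driven by estrogen-alone users will be presented as applying to both regimens. No section says so. The plan merely lacks anything that would guard against it.

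What the reply does not remove is the mismatch between the randomisation and the analysis, which costs almost nothing to close before unblinding and is less credible if closed afterwards.

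**Conclusion.** The point holds as a gap in prespecification. Both stratification factors are absent from the primary and all other analyses named in 12.2, and no estimate by HRT type is promised. It threatens neither type I error nor the sample size. The cost in precision is about 1-4% of the standard error if an assumed 2- to 4-point difference between HRT types exists in both arms, and about 0.2-0.9% if it exists only under letrozole. These figures rest on the pilot E+P share of one sixth and the planning SD of 5.5. The contribution of site cannot be sized, because the documents give neither the number of sites nor any between-site variation.

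The more useful gain is in reporting. An estimate by regimen would be descriptive only, and at about ±5.9 points for E+P users its main value is to show how little the trial can say about them. The documents do not establish a regimen difference in the eligible population, and the recommendation does not depend on one.

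**What to change.** In section 12.2:

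- Make the primary comparison a linear model of change in Ki-67 on treatment, HRT-type stratum and site, with baseline Ki-67 as a covariate in all cases. Pool small sites by a rule fixed before unblinding.
- If the skewness fallback is triggered, use a two-sample rank test stratified by HRT type (van Elteren). The signed-rank test now named does not compare two independent groups.
- Use the same stratum terms for the continuous secondary endpoints.
- Report the letrozole-placebo difference with 95% CI within each HRT type, and the interaction estimate, labelled descriptive.
- State that at the pilot share (about 16 of 96 women) the E+P interval would be about ±5.9 points, so no efficacy claim specific to E+P users can be made.

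The cost is SAP wording and a few degrees of freedom. HRT type and site are known for every woman at randomisation, so data collection and sample size do not change.
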